ImpACt of very high protein Content enteral nUtrition formulas on protein metabolism and residual gastric volume in critically ill MUltipLe trAuma paTiEnts – ACCUMULATE trial -

Study Protocol

Imp**AC**t of very high protein **C**ontent enteral n**U**trition formulas on protein metabolism and residual gastric volume in critically ill **MU**ltip**L**e tr**A**uma pa**T**i**E**nts

- ACCUMULATE trial -

Background and rationale:

Despite an increased survival among critically ill patients, many of the ICU "survivors" may develop prolonged functional disabilities(1). It has already been proven that nutritional therapy is essential, considering that an adequate provision of calories and proteins may influence patients prognostic(1).

Multiple trauma patients are on a particular nutritional risk, since their high nitrogen demands and associated nutritional therapy challenges, caused by repeated surgical intervention or multiple imagistic procedures(2). Although nutritional therapy impact on mortality is still in debate, clear, positive results were obtained in decreasing ICU and hospital stay after adequate nutritional support(3).

According to ESPEN guideline on clinical nutrition in the ICU early enteral nutrition (within 48 h) should be initiated in order to assure an adequate calorie and protein intake(4). Beside optimal timing, the management of nutrition therapy in critically ill patients should also integrate the optimal route and caloric/protein targets(4).

Energy requirements monitoring through indirect calorimetry has been proposed as a standard-of-care method for critically ill patients, considering its proven superiority towards predictive equation(5).

Beyond calorie intake, proteins proved to play a central role in maintain lean body mass, healing wounds and supporting immune function(5). For multiple trauma patients it was reported that protein losses may reach 14% of the total body stores, thus this type of patients are exposed to a particular increased risk of protein deficits(6). If calorie administration benefits from a proper monitoring tool, protein requirements are still based on predictive equation(6). The impact of protein administration is also lacking of direct measurements techniques(7). Lean body mass evaluation by ultrasound and computerized tomography has been reported to have a good correlation with hospital stay and pots-ICU functional capacity(7). Moreover muscle function evaluation through a hand-grip dynamometer was also tested with good results in patients with ARDS(7).

Source of administered protein may also influence nitrogen balance, considering that whey proteins (rich in leucine) promote a slower hydrolysis and allow a longer period for absorption(8).

Reaching the recommended goals is often impeded by gastric intolerance manifested through increased gastric volume residues(4). It has been already demonstrated that large gastric volume residues are associated with impaired absorption and an increased incidence of aspiration pneumonia(9).

Gastrointestinal dysfunction in multiple trauma patients admitted to the intensive care unit (ICU) is an important yet underrecognized consequence(10). There are various

causes of gastrointestinal tract dysfunction mostly related to patients general health condition and to their diagnostics(11). Gastrointestinal failure may be induced by several factors like immunological, biological and mechanical barrier disruption and it may be manifested through stress ulceration, bacterial translocation, ileus, intra-abdominal hypertension, diarrhoea and constipation(2).

Whether residual gastric volume monitoring should be regularly performed has been extensively discussed. Although the results from some randomised trials which focused on monitoring gastric residual volume, did not find any difference in outcomes, this measurement was far for being abandoned(12). Moreover, gastric residual volume monitoring is still an essential component of enteral nutrition patient care(13).

Although several monitoring methods for gastric volume residue measurements were described, there is no generally accepted technique for daily use(12,13).

Body composition monitoring

Objective:

This prospective observational randomized study aims to determine energy, protein intake and gastrointestinal tolerance while using enteral nutrition formulas with very high protein content and enteral nutrition formulas with normal protein content.

Outcomes will be assessed as:

Primary outcome parameter:

- Differences regarding achieving protein and calorie daily targets in grams per kilogram of body weight (g/kg BW) at day 5 of the intervention period and at day 10 when using enteral nutrition formulas with different protein content
- Differences regarding residual gastric volume when using enteral nutrition formulas with different protein content

Secondary outcome parameter:

Differences regarding body composition when using enteral nutrition formulas with different protein content:

- a) Quadriceps rectus femoris thickness measured by B-mode ultrasonography on admission, on day 5, on day 10 and 15.
- Body composition assessment (Fat-Free mass, Total Body water, Phase angle) using bioimpedance analysis after patient has been stabilized (24 hours after extubation and on day 5 after extubation)
- c) Plasmatic levels of prealbumin and inflammatory markers (C reactive protein) on day 5 and on day 10;
- d) Muscle function evaluation using handgrip dynamometer after extubation and sedation cessation. (24 hours after extubation and on day 5 after extubation)

Safety points:

- Clinical parameters vomiting, diarrhoea
- Biochemical parameters base excess, urea levels
- Daily gastric residual volume evaluation using ultrasound gastric antrum measurements after 24 hours of continuous enteral nutrition administration using both types of formulas;

Study population

Consecutive patients with multiple trauma intubated and mechanical ventilated, admitted to the intensive care unit (ICU).

Inclusion criteria:

- Adult patients (>18 yrs) admitted to the ICU
- Multiple trauma (Injury severity score > 18)
- Intubation and mechanical ventilation upon admission in ICU or during the first 24 hours of admission, for at least 48 h

Exclusion criteria

- Age < 18 years
- Pregnant women
- Patients not intubated or not mechanically ventilated or receiving only noninvasive ventilation
- o Patients with enteral feeding contraindication 48 h after admission
- o Patients with recent gastrointestinal surgical intervention
- Patients on chronic therapy with corticosteroids

Sample size calculation

Since the hypotheses of the study are exploratory, no formal sample size calculation has been performed. This prospective observational study aims to recruit >60 multiple trauma patients.

Randomization:

Simple randomization method will be used to assign subjects into two groups A and B.

Group A – Nutrison Protein Plus with 6.3 g/100 ml protein

Group B - Nutrison Protein Intense with 10 g/100 ml protein

Ethical considerations:

This study will be conducted in full conformity with the Declaration of Helsinki and Good Clinical Practices.

Local ethical committee approval will be asked before any patient will be included.

Considering that nutritional support has become a standard-of-care in every intensive care unit in the world, it is considered that this research is based on collecting data routinely available for every critically ill patient. Although no intervention is performed an informed consent will be provided.

Taking into account that the included patients are not able to provide informed consent at the time of recruitment (on ICU admission), a Power of Attorney or a Legal tutor will act as Consultee and will be asked to consent/decline participation to the study on legal behalf of the patient. If patients have Advance Decision Plan including participation in research studies the Plan will be respected and recruitment pursued/abandoned accordingly.

After regaining capacity, all patients will be asked to provide Informed Consent for using their personal data and will be given the possibility to:

- Provide Informed Consent for the acute data and follow-up.
- Deny research participation and request destruction of acute data collected.

Study participant research data, which is for purposes of statistical analysis and scientific reporting, will be transmitted to the Data Manager and the Statistician of the study.

Expected impact of the study

KNOWLEDGE

Investigators aim to provide a detailed description of protein administration using two different types of enteral formulas. The main objectives of the study are to evaluate energy, protein intake and gastrointestinal tolerance while using enteral nutrition formulas with different protein content. Nevertheless, investigators want to provide data about the impact of these different enteral nutrition formulas on body composition as well as on functionality.

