## **Sample size calculation:**

- Expected difference ( $\Delta\Delta$ ) = 0.4 g/kg BW
- Standard deviation ( $\sigma\sigma$ ) = 0.5 g/kg BW
- Significance level ( $\alpha\alpha$ ) = 0.05
- Power ( $1-\beta 1-\beta$ ) = 0.80
- With an expected difference of 0.4 g/kg BW and a standard deviation of 0.5, a minimum sample size of 25 per group is required.
- To ensure robustness and account for drop-outs and variability, targeting at least 28 participants per group is recommended.

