### **3. Secondary Outcome Analysis:**

- Changes in quadriceps rectus femoris thickness over time will be analyzed using repeated measures ANOVA or mixed-effects models.
- Differences in body composition parameters (Fat-Free Mass, Total Body Water, Phase Angle) will be analyzed using paired t-tests or Wilcoxon signed-rank tests for within-group comparisons and independent t-tests or Mann-Whitney U tests for between-group comparisons.
- Differences in plasmatic levels of prealbumin and C-reactive protein will be analyzed using independent t-tests or Mann-Whitney U tests.
- Differences in handgrip strength will be analyzed using paired t-tests or Wilcoxon signed-rank tests for within-group comparisons and independent t-tests or Mann-Whitney U tests for between-group comparisons.

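### Prealbumin and CRP have no scheduled admission value, and urea and base excess no stated sampling time, so a chance imbalance between groups can be neither seen nor adjusted for

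*Protocol*

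**What the plan says.** - Protocol, secondary outcome parameter c): "Plasmatic levels of prealbumin and inflammatory markers (C reactive protein) on day 5 and on day 10". No earlier sample is listed.
- Protocol, secondary outcome parameter a), in the same list: "Quadriceps rectus femoris thickness measured by B-mode ultrasonography on admission, on day 5, on day 10 and 15". This outcome does have an admission value.
- Protocol, Safety points: "Biochemical parameters base excess, urea levels". No day or frequency is attached to either marker.
- SAP, section 3 (Secondary Outcome Analysis): "Differences in plasmatic levels of prealbumin and C-reactive protein will be analyzed using independent t-tests or Mann-Whitney U tests". No covariate is named. For muscle thickness, the same section plans repeated-measures ANOVA or mixed-effects models.
- SAP, section 1 (Descriptive Statistics), promises summaries of all continuous variables, which would cover urea and base excess. No between-group comparison of them appears in the SAP text available. The part of the SAP before its sample size section could not be read, so it cannot be excluded that a schedule stands there.
- Protocol, Randomization: "Simple randomization method will be used to assign subjects into two groups A and B". No stratification is mentioned.
- Protocol, Ethical considerations: "this research is based on collecting data routinely available for every critically ill patient".

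**The concern.** All four markers reflect the injury, shock and kidney function that a patient brings to the unit before any study formula is given. With an admission value, that part of the variation can be removed from the comparison. Without one, it stays in the error term, and nobody can tell afterwards whether the groups happened to differ at the start.

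This matters most for urea. The two formulas differ in protein content (6.3 against 10 g per 100 ml), and urea is the listed safety marker most directly tied to protein load. A safety marker with no sampling time and no visible comparison is weak support for the change in local and national recommendations that the protocol expects. An admission value that is not captured at the time may not be recoverable later.

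**Working it through.** **The plan's own figure.** The SAP states that with "an expected difference of 0.4 g/kg BW and a standard deviation of 0.5, a minimum sample size of 25 per group is required". Using two-sided alpha 0.05 and power 0.80:

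n = 2 × (1.960 + 0.842)² × 0.5² / 0.4² = 24.5, rounded up to 25 per group.

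The figure reproduces. The target of 28 allows for a loss of 1 − 25/28 = 10.7%. This calculation concerns protein intake. The documents give no sample size reasoning for the four blood markers, so it serves here only to fix the group size.

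**Inputs for the check.** 28 per group (SAP), or about 30 per group (protocol, more than 60 in total), with equal groups assumed. The correlation r between the admission and the later value is not given, so r = 0.3, 0.5 and 0.7 are assumed.

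**Step 1: size of a chance admission difference.** In units of the patient SD, its standard deviation is sqrt(2/n).

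- n = 28: sqrt(2/28) = 0.267; n = 30: sqrt(2/30) = 0.258.
- Probability that it exceeds 0.25 SD in either direction: 35% (n = 28) and 33% (n = 30).
- Probability that it exceeds 0.5 SD: 6% (n = 28) and 5% (n = 30).

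**Step 2: what is carried to follow-up.** An admission difference of 0.25 SD shifts the expected later difference by r × 0.25, which is 0.075 SD at r = 0.3 and 0.175 SD at r = 0.7. Either is less than one standard error of the group difference (0.26 to 0.27 SD).

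**Step 3: is the unadjusted test valid?** In 40,000 simulated trials at each r (28 per group, no formula effect, normal data), the mean group difference was about 0.00. The type I error was 0.053, 0.051 and 0.049 for r = 0.3, 0.5 and 0.7, so the test is valid over repeated randomisations. Among the roughly 6% of trials with an admission difference above 0.5 SD, the false-positive rate was 10%, 17% and 29%. Under the stated schedule, such a trial could not be recognised.

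**Step 4: gain from adjustment at 28 per group.** With the admission value as covariate, the variance of the group difference is multiplied by 1 − r². The difference detectable with 80% power is 2.80 × 0.267 = 0.75 SD unadjusted, and 0.75 × sqrt(1 − r²) adjusted. The equivalent unadjusted group size is 28 / (1 − r²).

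| Assumed r | Variance cut | Detectable difference | Equivalent unadjusted n per group |
|---|---|---|---|
| 0.3 | 9% | 0.71 SD | 31 |
| 0.5 | 25% | 0.65 SD | 37 |
| 0.7 | 49% | 0.53 SD | 55 |

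**The case against.** The strongest reply is that allocation is randomised. A reader might infer that chance differences in injury enter the result as if they were effects of the formula. The documents do not support that: the error rate and the confidence interval of the unadjusted test already allow for chance imbalance, as Step 3 shows. This part of the reply stands in full.

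A reader might also infer that urea and base excess have no admission value. The protocol does not say so. It gives no time points for them at all, and since it describes the data as routinely available, admission values may well exist. The documented gap is unspecified timing.

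Three further replies carry some weight. Injury severity is known at entry and could serve as a covariate; but none is planned, and an anatomical score is a poor substitute for each marker's own starting value. The gain depends on an assumed correlation and is small at the lower end (9%). And these are secondary and safety measures in a study that calls its hypotheses exploratory.

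Renal replacement needs care too. Renal failure is not among the exclusion criteria, and renal replacement lowers urea. It would be tempting to drop values taken after it starts. That would condition on an event after randomisation which the formula might influence, and would remove the patients of most concern. An admission value does not solve this problem either.

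**Conclusion.** The point holds as a matter of precision and specification. Prealbumin and CRP have no scheduled admission value and are to be compared unadjusted, although another outcome in the same list has a baseline. Urea and base excess lack a stated sampling time and, in the SAP text available, a between-group comparison.

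At 28 to 30 per group, a chance admission difference above 0.25 SD would arise in about a third of trials, and the plan offers no way to see it or adjust for it. Adjustment would cut the variance by 9 to 49% for assumed correlations of 0.3 to 0.7. These figures rest on equal groups, approximate normality (after transformation where needed) and that assumed range. The validity of the tests and the primary outcomes, intake and residual gastric volume, are not in question. The change is worth making because it is cheap and cannot easily be made afterwards.

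**What to change.** **Protocol, Secondary outcome parameter c) and Safety points.** Add an admission value, taken before the first study feed, for CRP, urea and base excess from routine admission bloods, and for prealbumin where an admission sample can be assayed. State days 5 and 10 as the comparison times for urea and base excess.

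**SAP, section 3, with a matching entry for the safety markers.** Compare each of the four markers between groups at day 5 and at day 10 by a linear model with the admission value as covariate. Use the log scale for skewed markers such as CRP. Report the adjusted difference with its 95% confidence interval.

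**Renal replacement.** Report its use by group descriptively, beside the urea and base excess results, and do not exclude values taken after it starts.

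**Cost.** A few lines of schedule and SAP text, plus one added prealbumin assay per patient. The documents describe no sample storage and no study funding, so that assay may not always be possible. Where it is not, the other three markers can still be adjusted.

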### **2. Primary Outcome Analysis:**

- Differences in protein and calorie intake between the groups at day 5 and day 10 will be analyzed using independent t-tests or Mann-Whitney U tests, depending on the data distribution.
- Differences in residual gastric volume between the groups at day 5 and day 10 will be analyzed using independent t-tests or Mann-Whitney U tests.

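### Gastrointestinal tolerance is a main objective, but only residual gastric volume has a planned group comparison: vomiting and diarrhoea have none, and no rule covers gastric readings when feeding is interrupted

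*Protocol*

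**What the plan says.** - **Objective.** Under Objective, the protocol "aims to determine energy, protein intake and gastrointestinal tolerance while using enteral nutrition formulas with very high protein content". Under Expected impact of the study it repeats the aim: "The main objectives of the study are to evaluate energy, protein intake and gastrointestinal tolerance".
- **Primary outcome.** The tolerance item under Primary outcome parameter is "Differences regarding residual gastric volume when using enteral nutrition formulas with different protein content". It names no day, method or feeding condition.
- **Measurement.** The only description is under Safety points: a daily evaluation by "ultrasound gastric antrum measurements after 24 hours of continuous enteral nutrition administration using both types of formulas".
- **Other tolerance events.** Safety points also lists "Clinical parameters vomiting, diarrhoea", with no definition, grading or time window.
- **Analysis.** SAP section 2 states: "Differences in residual gastric volume between the groups at day 5 and day 10 will be analyzed using independent t-tests or Mann-Whitney U tests". SAP section 3 (secondary outcomes) names no tolerance measure. Section 1 promises frequencies and percentages for categorical variables in general. Section 4 plans multiple imputation or other suitable methods with unspecified sensitivity analyses, and does not mention interrupted feeding.

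SAP text ahead of its sample size section was not available for this review. The analysis sections, numbered 1 to 5, run on without a visible gap.

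**The concern.** Two separate things are at stake.

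**Coverage.** The protocol's background lists diarrhoea among the ways gastrointestinal failure shows itself. A scan of the gastric antrum does not capture it. If one formula caused more diarrhoea or vomiting but left similar gastric volumes, the only planned tolerance comparison could find nothing, and the trial could call the formulas equally tolerated. The protocol expects its results to change local and national recommendations, so that statement would be used.

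**Selection.** The background also says: "Reaching the recommended goals is often impeded by gastric intolerance manifested through increased gastric volume residues". Large residues and failure to reach feeding goals are therefore linked in the protocol's own reasoning. If a scan counts only after 24 hours of unbroken feeding, the days without a reading would tend to be those with the largest volumes. The group with worse tolerance would lose more of them, which pulls the observed difference toward zero.

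**Working it through.** **1. The plan's own figure.** The SAP's sample size uses a difference of 0.4 g/kg, SD 0.5, alpha 0.05 (taken as two-sided) and power 0.80: n = 2 × [0.5 × (1.960 + 0.842) / 0.4]² = 24.5, so 25 per group. It reproduces. It concerns intake; no tolerance measure was sized.

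**2. Where each tolerance measure is analysed.**

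| Measure | Collected (protocol) | Group comparison (SAP) |
|---|---|---|
| Residual gastric volume | Primary outcome; daily scan under Safety points | Section 2, days 5 and 10 |
| Vomiting | Safety points | None; at most section 1 frequencies |
| Diarrhoea | Safety points | None; at most section 1 frequencies |
| Feed interrupted for intolerance | Not listed | None |

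**3. What the measurement wording can mean.** It can be (a) a condition before each daily scan, (b) a start point, with daily scans once the first 24 hours of feeding are complete, or (c) a description of how feed is delivered. The primary outcome and SAP section 2 carry no such condition. Only (a) loses readings.

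**4. Size of the loss under reading (a).** Everything here is assumed, because the documents give no interruption rates. Gastric volume is normal with SD 1, mean 0 in one group and d in the other. Feed is interrupted, and the reading lost, when an index with correlation r to volume exceeds a common cut c. The cut interrupts a proportion p of the first group, so c = z(1 − p). With φ and Φ the normal density and distribution function, the mean among patients still measured is:

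- first group: −r φ(c)/Φ(c)
- second group: d − r φ(c − rd)/Φ(c − rd)

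Example: d = 0.5, p = 0.10, r = 1, c = 1.2816. The first group's mean is −0.195 and the second's is 0.5 − φ(0.7816)/Φ(0.7816) = 0.124. The observed difference is 0.319, and 1 − 0.319/0.5 = 36% is lost. Interruption is 10% versus 21.7%.

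| True d | r | Observed difference, p = 10% to 30% | Understatement |
|---|---|---|---|
| 0.5 | 0.5 | 0.46 to 0.43 | 8% to 14% |
| 0.5 | 1 | 0.32 to 0.21 | 36% to 57% |
| 0.8 | 0.5 | 0.73 to 0.69 | 9% to 14% |
| 0.8 | 1 | 0.48 to 0.32 | 40% to 61% |

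The direction is the same throughout; the size depends on assumptions that the documents cannot settle.

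**5. Whether ranking interrupted patients worst recovers the comparison.** The Mann-Whitney test targets P(second > first) plus half of any ties. For d = 0.5, p = 0.10 and r = 1, the value with complete readings is Φ(0.5/√2) = 0.638. Let J be the integral of φ(x − d)Φ(x) up to c, and let A = Φ(c) and B = Φ(c − d) be the proportions still measured. Among measured patients the value is J/(AB) = 0.611. With interrupted patients tied at the worst rank it is J + (1 − B)A + ½(1 − A)(1 − B) = 0.637, almost all of the signal.

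**6. What an event comparison can deliver at 28 per group.** The event rates are assumed. Power uses the normal approximation for two proportions, two-sided 0.05. The 95% half-width is 1.96 × √[(p₁(1 − p₁) + p₂(1 − p₂))/28].

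| Rates | Power at 28 per group | n per group for 80% power | 95% half-width |
|---|---|---|---|
| 10% v 30% | 0.46 | 62 | 20 points |
| 20% v 40% | 0.37 | 82 | 23 points |
| 30% v 50% | 0.33 | 93 | 25 points |
| 20% v 30% | 0.14 | 294 | 23 points |

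The result would be an estimate with a wide interval, not a powered test.

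**The case against.** A reader might infer that interrupted patients are excluded from the gastric-volume comparison. The documents do not say so. The measurement wording has two other natural readings, the primary outcome and the SAP test are unconditional, and nothing states that a scan is skipped when feed stops. The loss is a risk created by ambiguous wording, not a stated feature of the design.

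A reader might also infer that interrupted patients escape every comparison, or that vomiting and diarrhoea will be reported only for both groups pooled. Neither is supported. Interruption would lower protein and calorie intake, a compared primary outcome, and SAP section 1 does not say its frequencies are pooled; tables by group are just as plausible. Intake is still a poor stand-in for tolerance. The background attributes feeding difficulty in these patients to surgery and imaging as well, and the formulas differ in concentration (6.3 versus 10 g protein per 100 ml), so more protein can be delivered despite more interruption.

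SAP section 4 plans imputation. That helps when missingness depends on recorded data. If a reading is missing because the volume was high, imputing as missing at random fills it from patients with lower volumes, so the bias remains in part.

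Descriptive reporting of safety events is defensible in a study whose hypotheses are called exploratory, and the power figures show how little a test could add. This stands against a formal test, but not against an effect estimate with its interval for a stated main objective.

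**Conclusion.** The point holds on coverage. In the available SAP text, a main objective is compared through one gastric measure only, and vomiting and diarrhoea lack any planned between-group estimate. This needs no assumption beyond the unavailable SAP text not supplying one.

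On selection it holds conditionally. If continuous feeding is required before each scan, and interrupted days are left missing or imputed as missing at random, the gastric-volume difference is biased toward zero. For a true 0.5 SD the understatement is about 8% to 57% across the assumed scenarios (up to 61% for 0.8 SD). No single figure within that range can be defended from the documents. The stronger statement, that the least tolerant patients will drop out and the groups will look alike, goes too far: the loss itself is not established, and even the scenarios that assume it leave a visible difference.

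The change should be made, but it does not undermine the intake results.

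**What to change.** 1. **Event comparison.** Add to the SAP a between-group estimate, in all randomised patients, of the proportion with vomiting and the proportion with diarrhoea during study feeding, each as a risk difference with 95% confidence interval, plus event days per feeding day. Define both events. Present this as estimation, not as a powered test. Base any tolerance conclusion on it together with gastric volume.
2. **Measurement wording.** Reconcile the Safety points description with the unconditional primary outcome and SAP section 2, so that it is clear whether continuous feeding is a condition, a start point or a mode of delivery.
3. **Interrupted feeding.** Record feed status at each scan and the reason for any interruption. Add a sensitivity analysis of gastric volume that keeps patients with feed interrupted for intolerance in the comparison, for example ranked worst in the Mann-Whitney test. Do not leave them missing, and do not take a later reading at face value: a scan after feed has been off may show a partly emptied stomach and give the least tolerant patients low values.

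Cost: protocol and SAP wording, event definitions, a count of feeding days, fields for feed status and reason for interruption, and a little more analysis. Vomiting and diarrhoea are already collected and the scan is already daily.

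### Simple randomisation does not reliably deliver the SAP's per-group size: at 61 patients an arm starts below the recommended 28 in 44% of trials and below the required 25 in 12% (minor; little effect on power)

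*Protocol*

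**What the plan says.** The protocol, under Randomization, says: "Simple randomization method will be used to assign subjects into two groups A and B". Under Sample size calculation it says that no formal calculation was made because the hypotheses are exploratory, and gives only a total: "This prospective observational study aims to recruit >60 multiple trauma patients". No upper limit is set.

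The SAP, under Sample size calculation, does calculate a size and expresses it per group: "a minimum sample size of 25 per group is required". To allow for drop-outs and variability it adds: "targeting at least 28 participants per group is recommended". So 25 is the stated requirement and 28 is a recommended target.

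The supplied text gives no allocation ratio, no blocking or other balance rule, and no rule to continue recruitment until both arms reach a set size. The part of the SAP before its sample size section was not available for this review.

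**The concern.** A per-group size is a statement about the smaller arm. Simple randomisation assigns each patient independently, so it fixes the total and leaves the split to chance. With about 60 patients, chance differences of several patients between arms are ordinary. The protocol's allocation method and the SAP's per-group figure therefore do not fit together: the trial can recruit its planned total and still report an arm smaller than the SAP says is needed, even before anyone drops out.

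What is at stake is mainly whether the trial meets its own stated group size. Whether power suffers is a separate question, and the working below treats it separately.

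**Working it through.** **Inputs**
- Allocation: simple, two groups (protocol, Randomization). A 1:1 ratio is assumed, since none is stated; the SAP's equal group sizes suggest it.
- Total: more than 60 (protocol, Sample size calculation), so 61 is the smallest total that qualifies.
- Per-group size: 25 required, at least 28 recommended (SAP, Sample size calculation).
- Difference 0.4 g/kg, SD 0.5 g/kg, alpha 0.05, power 0.80 (same SAP section). Two-sided testing is assumed. It reproduces the SAP's figure; one-sided testing would give 20.

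**Step 1. Reproduce the SAP's figure.** The normal-approximation formula is

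n per group = 2(z₀.₉₇₅ + z₀.₈₀)² σ² / Δ² = 2(1.960 + 0.842)² × 0.25 / 0.16 = 24.5, rounded up to 25.

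This matches the SAP. (The exact t-test needs 25.5, that is 26; the gap is immaterial here.) No drop-out rate is stated. Going from 25 to 28 implies 1 − 25/28 = 3/28 = 10.7%.

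**Step 2. Chance that the smaller arm misses the stated size.** With A ~ Binomial(N, 0.5), P(smaller arm < k) = 2 × P(A ≤ k − 1).

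| Total N | Smaller arm below 28 | Smaller arm below 25 |
|---|---|---|
| 61 | 44.3% | 12.4% |
| 65 | 21.5% | 4.6% |
| 70 | 7.2% | 1.2% |
| 72 | 4.4% | 0.6% |

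Simple randomisation would need about 72 patients for a 95% chance of at least 28 in both arms.

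**Step 3. The same question after drop-out, N = 61.** Assume each patient drops out independently with probability d. For a split a/b, the chance that an arm ends with fewer than 25 completers is

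1 − P(Bin(a, 1 − d) ≥ 25) × P(Bin(b, 1 − d) ≥ 25).

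For simple randomisation this is averaged over the binomial distribution of splits. Because the rate is an assumption, a range is shown.

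| Drop-out d | Simple | 30/31 split | 29/32 split |
|---|---|---|---|
| 5% | 25% | 0.4% | 1.4% |
| 10% | 45% | 10% | 17% |
| 10.7% (implied) | 48% | 13% | 21% |
| 15% | 69% | 41% | 50% |

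The 29/32 column is the worst split possible with blocks of 4 and 6. A block of 6 stopped part-way can leave the arms at most 3 apart, and 61 = 29 + 32. At 15% drop-out even balanced arms often end below 25, so blocking removes only the part of the shortfall that comes from the split.

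**Step 4. Effect on power.** Exact two-sided t-test with d = 0.4/0.5 = 0.8, N = 61, no drop-out:

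| Split | Power |
|---|---|
| 30/31 | 86.7% |
| 27/34 | 86.3% |
| 25/36 | 85.6% |
| 24/37 | 85.1% |
| 20/41 | 82.3% |
| 18/43 | 80.0% |

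Averaged over all splits under simple randomisation, power is 86.1%, a loss of 86.7 − 86.1 = 0.6 percentage points. The chance of a split worse than 18/43, where power would drop below 80%, is 2 × P(A ≤ 17) = 0.07%.

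With about 54 completers (61 × 25/28 = 54.5), power is 82.2% at 27/27, 80.9% at 22/32 and 79.6% at 20/34.

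**The case against.** The strongest reply is that a short arm costs almost nothing, because the other arm gains the patients that it lacks. A 24/37 split falls short of the SAP's 25 per group yet has 85.1% power, more than the 79.1% of the SAP's own 25/25 or the 83.6% of 28/28 by the same exact test. This stands. It limits the point to whether the stated group size is met.

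It can also be said that simple randomisation is valid, unbiased and the least predictable method. That matters here, because the two products are identified by name and the supplied text describes no blinding. This also stands, as a small price of blocking. Finally, the protocol calls its hypotheses exploratory and sets no upper limit, so recruitment beyond 61 would shrink the problem. True, but nothing in the supplied text commits the trial to a larger total, and the SAP's per-group figure remains in force.

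Three stronger readings are tempting, and the documents do not support them:
- **That 28 is the SAP's minimum.** The SAP's minimum is 25; 28 is recommended. Against the actual minimum, the starting shortfall at 61 patients is 12%, not 44%.
- **That the trial is underpowered because of its allocation method.** Step 4 of the working shows otherwise.
- **That unequal arms undermine the planned t-test.** That requires unequal variances as well, and the SAP gives a single SD. If unequal variances were a worry, Welch's test would deal with them directly.

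**Conclusion.** The concern holds as a minor inconsistency. Simple randomisation of the smallest total that satisfies the protocol does not reliably give the per-group size that the SAP states: 44% of trials start with an arm below the recommended 28 and 12% with an arm below the required 25. At the implied drop-out, about 48% end with an arm below 25 completers, against 13% to 21% with blocked allocation.

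The figures rest on 1:1 allocation and a total of 61. The power figures also assume two-sided testing, and the completer figures assume independent drop-out at about 10.7%. None of these assumptions is stated in the supplied text. A larger total weakens the point quickly. The unavailable part of the SAP might say more about randomisation.

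**What to change.** In the protocol's Randomization section, replace simple randomisation with concealed 1:1 permuted-block randomisation using randomly varying block sizes, for example 4 and 6. With 61 patients, each arm then has at least 29, which meets the SAP's recommended 28 with no increase in the total.

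The cost is a new computer-generated allocation list and a short protocol change. The downside is slightly greater predictability of the next assignment in what appears to be an open trial. Varying the block sizes and not disclosing them to recruiting staff limits it.

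If simple randomisation is kept, the SAP should restate its sample size as a total and report the chance of missing 28 per group at that total.
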